6.11.2.3 Change from Baseline in pain (assessed using the NRS-11 and PII)

6.11.2.3.1 NRS-11

All NRS-11 records will be listed by participant and visit.

The number and percentage of participants in each of the result categories (Appendix 1.3) at baseline will be summarized. Absolute values and change from baseline will be summarized overall and by confirmed objective response status (as defined with confirmed response rate in Section 4.1.1 using adjudicated values where appropriate), by visit and age cohort, the summaries presented will be number and percentage of participants with a non-missing score, mean, SD, median, minimum, and maximum values.

For NRS-11, a within-patient meaningful score change, or meaningful score difference (FDA, 2023), will be derived by anchor-based analysis of the study's data as described in the meaningful change threshold analysis plan (Version 1.0, dated 12Sep2023). The primary focus of this will be on if such a relevant difference exists at Cycle 13.

Additionally the number and percentage of participants with a change representing a clinically meaningful improvement (alongside associated Clopper-Pearson confidence intervals) will be presented using change from baseline of ≤ -1 (This cut point has previously been researched and assessed as a meaningful change in pediatric populations (Hirschfeld, 2014)), representing a clinically meaningful improvement, will be presented, as well as change from baseline greater than the within-patient meaningful change threshold (i.e., derived by anchor-based analysis of the study's data in accordance with the MCT SAP; see Section 5.8 above) will be presented.

In addition, within each age cohort, the proportion of participants reaching the anchor-based and distribution threshold will be analyzed in the subgroup of participants who have a confirmed objective response status versus the subgroup of those who do not. This is to further characterize the relationship between PRO improvement and the clinical endpoint of tumor response. The proportion of participants reaching the anchor-based (and distribution) thresholds will be summarized with 95% Clopper-Pearson Cls by confirmed objective response status, and the differences in the proportions of participants reaching the anchor-based/distribution thresholds between responders and non-responders will be tested using a Chi-Square test at a 5% significance level.

An MMRM will be fit separately by age cohort with change from baseline in NRS-11 score as the dependent variable, visit as a fixed effect and baseline NRS-11 score as a covariate. The covariance structure will be decided in the manner described in Section 6.11.2.2, and a Kenward-Roger approximation will be used for the degrees of freedom. This model will be fitted twice, once using only data through Cycle 13, and once through Cycle 24. EOT visits will be mapped to the closest scheduled tumor visit following the rules outlined in Table 13, and will only be included in the model if the participant has no other record at that timepoint. LS Means estimates will be presented with associated standard errors, 95% Cls and p-values by visit. Plots of the LS Means estimates over time with associated 95% Cl bands will be presented separately by age cohort for both models.

Box and whiskers plots of change from baseline will be presented by visit and confirmed objective response status for each age cohort separately.

A waterfall plot of change from baseline in NRS-11 will be presented by visit for adult cohort, pediatric cohort self-report and pediatric cohort parent proxy separately at Cycles 5 and 13, with a line representing the respective within-patient meaningful change threshold derived by anchorbased analysis. This plot will be color-coded by confirmed objective response status.

Document: S:\Q_146\Q_03974\MEK-NF-201\Prog_Stat\Documentation\SAP\MEK-NF-201 SAP v1.0.0.docx
Author:

Additionally, a sensitivity analysis will be performed on the NRS-11 results using the imputed data described in Section 5.5.1.2. The MMRM analysis described above will be performed with data up to Cycle 13. LS Means estimates, associated standard errors, 95% Cls and p-values will be presented by visit.

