2.2 Study Design

MEK-NF-201 is a multi-center, open-label, single-arm, longitudinal, uncontrolled, Phase 2b study to evaluate the efficacy, safety, and tolerability of mirdametinib in participants ≥ 2 years of age with an inoperable NF1-associated PN that is causing significant morbidity.

This study will consist of two phases: the Treatment Phase and the optional Long-Term Follow-Up (LTFU) Phase. Approximately 100 participants will be enrolled and stratified by age (approximately 50 participants 2 to 17 years of age and 50 participants ≥ 18 years of age). The first five participants enrolled in the pediatric cohort must be 9 to 17 years of age at the time of signing informed consent/assent. After the first 5 participants have enrolled in the pediatric cohort, enrollment into this cohort will be paused, and only after Data Monitoring Committee (DMC) evaluation of at least 2 cycles of cumulative safety data for these 5 participants will the pediatric cohort be re-opened and potentially expanded down to 2 years of age. Note the adult cohort will not be affected by this special procedure; participants ≥ 18 years of age will be enrolled continuously from the outset.

Document: S:\Q_146\Q_03974\MEK-NF-201\Prog_Stat\Documentation\SAP\MEK-NF-201 SAP v1.0.0.docx

Participants will be screened for up to 45 days prior to the first dose of study treatment (mirdametinib) and eligibility will be based on the inclusion and exclusion criteria listed in Sections 5.1 and 5.2 of the protocol, respectively. Study treatment will then be administered orally at a dose of 2 mg/m² BID with a maximum dose of 4 mg BID. Dosing in the Treatment Phase will be on a 28-day cycle with a 3 week on/1 week off schedule for up to 24 Cycles. Eligible participants will take their first dose of study treatment following all pre-dose assessments on Cycle 1 Day 1. All participants will remain in the Treatment Phase of the study until radiographic disease progression (confirmed by central review), they discontinue study treatment for any other reason, the study is stopped by the sponsor for any reason, or the participant has completed the study through Cycle 24.

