5.3 Covariates

No covariates will be considered for the primary efficacy analysis. For all mixed models for repeated measures (MMRM) used in secondary and exploratory analyses, the only covariate included will be the respective baseline score.

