An MMRM will be fitted separately by age cohort and questionnaire type for each PedsQL score listed in Section 4.1.2.2.1. Change from baseline in PedsQL score will be the dependent variable, visit will be fitted as a fixed effect, and baseline PedsQL score used as a covariate. Covariance structures will be trialed in the order of decreasing complexity, with the first structure that converges without error used. The structures tested are as follows: Unstructured, Heterogenous Toeplitz, Heterogenous Autoregressive, Autoregressive, Heterogenous Compound Symmetry, Compound Symmetry, Variance Components. A Kenward-Roger approximation will be used for the degrees of freedom. This model will be fitted twice, once using only data through Cycle 13, and once including data from the entire study (timepoints with < 5 subjects will not be presented). EOT and unscheduled visits will be mapped to the closest scheduled tumor visit following the rules outlined in Table 13, and will only be included in the model if the participant has no other record at that timepoint. For the MMRM change from baseline tables, the least square (LS) Means estimates will be presented with associated standard errors, 95% Cls and p-values by visit. Plots of the LS Means estimates over time with associated 95% Cl bands will be presented separately by age cohort and questionnaire type for both models.

Box and whiskers plots of change from baseline in total score will be presented by visit and confirmed objective response status for the adult cohort, pediatric cohort self-report, and pediatric cohort parent proxy separately.

A waterfall plot of change from baseline will be presented by visit for adult cohort, pediatric cohort self-report and pediatric cohort parent proxy separately for each PedsQL domain at Cycles 5 and 13 with a line representing the respective within-patient meaningful change threshold derived by anchor-based analysis. This plot will be color-coded by confirmed objective response status.

Additionally, a sensitivity analysis will be performed for each PedsQL score using the imputed data described in Section 5.5.1.1. The MMRM analysis described above will be performed with data up to Cycle 13. LS Means estimates, associated standard errors, 95% Cls and p-values will be presented by visit.

Document: S:\Q_146\Q_03974\MEK-NF-201\Prog_Stat\Documentation\SAP\MEK-NF-201 SAP v1.0.0.docx

Author:

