An MMRM will be fit separately by age cohort and questionnaire type, with change from baseline in PII score as the dependent variable, visit as a fixed effect and baseline PII score as a covariate. The covariance structure will be decided in the manner described in Section 6.11.2.2, and a Kenward-Roger approximation will be used for the degrees of freedom. This model will be fitted twice, once using only data through Cycle 13, and once through Cycle 24. Unscheduled and ET visits will be mapped to the closest scheduled tumor visit following the rules outlined in Table 13, and will only be included in the model if the participant has no other record at that timepoint. LS Means estimates will be presented with associated standard errors, 95% CIs and p-values by visit. Plots of the LS Means estimates over time with associated 95% CI bands will be presented separately by age cohort and questionnaire type for both models.

Box and whiskers plots of change from baseline will be presented by visit for adult cohort, pediatric cohort self-report and pediatric cohort parent proxy separately.

Document: S:\Q_146\Q_03974\MEK-NF-201\Prog_Stat\Documentation\SAP\MEK-NF-201 SAP v1.0.0.docx

Author:

A waterfall plot of change from baseline in PII will be presented by visit for adult cohort, pediatric cohort self-report and pediatric cohort parent proxy separately at cycles 5 and 13, with a line representing the respective within-patient meaningful change threshold derived by anchor-based analysis. This plot will be color-coded by confirmed objective response status.

Additionally, a sensitivity analysis will be performed on the PII results using the imputed data described in Section 5.5.1.2. The MMRM analysis described above will be performed with data up to Cycle 13. LS Means estimates, associated standard errors, 95% Cls and p-values will be presented by visit.

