6.11.3.6 Change in Tumor Volume

Target tumor volume, change from baseline in tumor volume, and percentage change from baseline in tumor volume calculated as per Section 5.1.2 will be summarized by the number of participants, mean, SD, median, minimum, and maximum values by visit for each age cohort separately. This will be presented by averaging the volume across the two readers (unless response adjudication was performed) and reported separately for each reader (A vs B) from the BICR data, since the volumetric measurement was not triggered for adjudication.

An MMRM will be fit separately by age cohort with change from baseline in tumor volume as the dependent variable, visit as a fixed effect and baseline tumor volume as a covariate. The covariance structure will be decided in the manner described in Section 6.11.2.2, and a Kenward-Roger approximation will be used for the degrees of freedom. This model will be fitted for each cohort for all scheduled visits up until the first point where there are fewer than 5 participants with valid tumor volume measurements. EOT visits will be mapped to the closest scheduled tumor visit following the rules outlined in Table 12 and will only be included in the model if the participant has no other record at that timepoint. LS Means estimates will be presented with associated standard errors, 95% Cls and p-values by visit. Plots of the LS Means estimates over time with associated 95% Cl bands will be presented separately by age cohort.

Best volumetric percentage change from baseline as well as the time, in months, to the best volumetric percentage change from baseline will be summarized by the number of participants, mean, SD, median, minimum, and maximum. This will be presented by averaging the volume across the two readers (unless response adjudication was performed) and reported separately for each reader (A vs B) from the BICR data. In addition, a waterfall plot of the best volumetric % change from baseline will be presented using the average (unless adjudication of response occurred), and by the two readers separately.

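### The single-arm PRO models treat the mean baseline as known, so the standard errors are too small for the population mean change; the size depends on a correlation the plan does not give

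*SAP*

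**What the plan says.** SAP Section 2.2 describes the trial: "MEK-NF-201 is a multi-center, open-label, single-arm, longitudinal, uncontrolled, Phase 2b study". Section 5.3 sets one rule for every mixed model: "the only covariate included will be the respective baseline score".

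The PRO models follow it, separately by cohort, and by questionnaire type for PedsQL and PII:

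- PedsQL (6.11.2.2): "visit will be fitted as a fixed effect, and baseline PedsQL score used as a covariate".
- NRS-11 (6.11.2.3.1): "change from baseline in NRS-11 score as the dependent variable, visit as a fixed effect and baseline NRS-11 score as a covariate".
- PII (6.11.2.3.2): "visit as a fixed effect and baseline PII score as a covariate".

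The NRS-11 output reads "LS Means estimates will be presented with associated standard errors, 95% Cls and p-values by visit", and the other two match it. Degrees of freedom use the Kenward-Roger approximation. Section 6.11.2.2 gives an ordered list of covariance structures, from unstructured down to compound symmetry and variance components, and the first that converges is used. The missing-data sensitivity analyses refit the same models.

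The exploratory volume model in 6.11.3.6 has the same form: "change from baseline in tumor volume as the dependent variable, visit as a fixed effect and baseline tumor volume as a covariate".

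The SAP does not say at what baseline value the least-squares means are evaluated. It gives no correlation between baseline and later scores, and no significance level for these p-values.

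**The concern.** In a randomized comparison the mean baseline drops out of the treatment difference, so conditioning on baseline is valid and gains precision. Here the reported quantity is the mean change itself. With complete data, the least-squares mean at the sample mean baseline is simply the raw mean change. Its model standard error uses only the residual variance after regression on baseline. The variation that comes from which baselines happened to be enrolled is still in the estimate but has been taken out of the standard error. A cohort that by chance enrols with worse scores than its population will drift back toward the population mean, and the interval does not allow for that.

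These models supply the only planned intervals and p-values for mean change in the secondary PRO endpoints, in a study that Protocol Section 9.2 presents as possibly supporting registration. What is at stake is intervals that are too narrow and p-values that are too small.

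**Working it through.** The plan gives no sample size, power or error rate for these models, so there is no figure of its own to reproduce.

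**Inputs from the documents.** One arm; about 50 participants per cohort (SAP 2.3); change regressed on visit and baseline; 95% intervals, which imply a nominal two-sided 5%.

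**Assumed inputs.** Baseline-to-visit correlation r, and the ratio k of follow-up SD to baseline SD. Neither is in the documents.

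**Step 1, variances.** Let s be the baseline SD and b the slope of change on baseline. The model variance of the mean change is (residual variance)/n. The full sampling variance is (residual variance + b²s²)/n. Kenward-Roger adjusts for estimating the covariance matrix, not for sampling of the baseline mean, so b²s²/n stays missing.

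**Step 2, equal SDs (k = 1).** The variance of change is 2s²(1−r), the residual variance is s²(1−r²), and the slope is r−1. So model SE / correct SE = √((1+r)/2), and the actual level is 2(1−Φ(1.96 × ratio)). For r = 0.5, the residual variance is 0.75s² and the missing term is 0.25s², which add to s². The ratio is √0.75 = 0.866. Then 1.96 × 0.866 = 1.697, which gives 9.0%.

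**Step 3, check by simulation.** 10,000 trials per row, n = 50, five post-baseline visits, no true change, complete data, unstructured model with a common baseline slope, t on n−2 degrees of freedom in place of Kenward-Roger.

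| r | SE ratio | Level, formula | Level, simulated |
|---|---|---|---|
| 0.4 | 0.837 | 10.1% | 9.8% |
| 0.5 | 0.866 | 9.0% | 8.7% |
| 0.6 | 0.894 | 8.0% | 7.7% |
| 0.7 | 0.922 | 7.1% | 6.9% |
| 0.8 | 0.949 | 6.3% | 6.4% |
| 0.9 | 0.975 | 5.6% | 5.5% |

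With n = 25, relevant because NRS-11 is collected only from age 8, the results were similar (10.0% at r = 0.4, 5.6% at 0.9). Correlation decaying from 0.75 to 0.5 over the visits gave 8.0% at n = 50. A one-sample t on the raw change held 4.6-5.4% across the PRO scenarios.

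**Step 4, unequal SDs.** The ratio becomes √(k²(1−r²)/(1+k²−2kr)). At k = 0.7 and r = 0.5 this is √(0.3675/0.79) = 0.682, a level of 18.1%. For r from 0.3 to 0.9 the level is 17-21% at k = 0.7, 10-15% at k = 0.85 and 5.0-8.7% at k = 1.2.

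**Step 5, tumor volume.** With r = 0.98 and equal, constant variances the level is about 5.1%. With a skewed baseline (assumed coefficient of variation 0.5-1.5) and proportional change (assumed SD 15%), it is 5.9-11.9% at zero mean change. Interval non-coverage is 7-29% when the true mean change is −10% to −20%. The one-sample t itself misses 3.8-11.5% in these settings, so part of the failure is skewness.

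**The case against.** **The target may be conditional.** For the mean change given the observed baselines, the same models miss 4.4-5.4% of the time, which is about nominal, and the SAP does not spell out which target it means. The coverage result stands, but it does not rescue the plan. SAP Table 1 sets the objective as the drug's effect on quality of life and pain. The conditional target equals the population mean change plus b times the gap between sample and population mean baseline, so it can differ from zero with no change at all in the population.

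**The size is not a property of the plan.** A reader might infer that the p-values simply run at 7-10%. The documents do not support that, because the figure needs r of 0.4-0.7 with equal SDs. NRS-11 and PII visit scores are averages over up to seven days, which reduces noise, so higher correlations and a level nearer 5-6% cannot be excluded. Nor can shrinking SDs, which push it the other way.

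**The consequence is limited.** A reader might also infer that false claims of improvement will follow. The SAP states hypotheses only for the response rate (5.2). The 5% level in the PRO sections belongs to the chi-square comparison of tumor responders with non-responders. Meaningful-change proportions with exact intervals are untouched, and n, mean and SD of change are tabulated by visit, so the paired standard error can be recovered. All of this stands and lowers the stakes. It does not make the reported intervals right.

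**Conclusion.** The point holds for the PedsQL, NRS-11 and PII models, and for the refits of them in the sensitivity analyses. In one arm, with baseline as a fixed covariate, the standard error is too small for the population mean change whenever change depends on baseline. If SDs are equal, a nominal 5% test runs at about 7-10% for r of 0.4-0.7 and about 5.5-6.5% for r of 0.8-0.9. It runs higher if follow-up SDs shrink. All of these rest on assumed correlations and SDs.

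With complete data the point estimate does not change, and the responder proportions and the primary response rate are unaffected. The point concerns sampling error only: no choice of standard error removes regression to the mean that comes from enrolling symptomatic participants without a control.

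Tumor volume should be kept apart. A reader might carry the 7-10% figure over because the model has the same form, but the size there depends on assumed skewness and may lie near 5% or well above 10%. The analysis is exploratory.

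**What to change.** In SAP 5.3, 6.11.2.2, 6.11.2.3.1 and 6.11.2.3.2, model the scores themselves with baseline as one of the repeated outcomes, and report the visit-minus-baseline contrast with its standard error, interval and p-value. Use an unstructured covariance, under which baseline still informs missing visits.

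Do not carry over the present fallback list with model-based standard errors. In simulation (n = 50, five visits, complete data), compound symmetry with baseline as an outcome rejected about 11% when baseline-to-visit correlation was below visit-to-visit correlation (0.5 against 0.75, and 0.6 against 0.8). Variance components rejected under 1%. If the unstructured fit does not converge, use a robust (sandwich) standard error.

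Alternatively, keep the planned models and add b²s²/n to the squared standard error. In a one-visit check at n = 50 with r of 0.4-0.8, this brought the level to 4.6-4.9% with complete data, and to 4.3-4.8% with about 20% missing depending on baseline.

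Make the same change in the sensitivity models. For tumor volume (6.11.3.6), change the model and also analyse on a log or percent-change scale, since the model change alone does not repair it.

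The cost is SAP wording and modest programming. PRO intervals widen by about 8-20% for r of 0.7 down to 0.4 (1/0.922 = 1.085; 1/0.837 = 1.195). The unstructured matrix grows from 15 to 21 parameters through Cycle 13 and from 36 to 45 through Cycle 24, so non-convergence becomes somewhat more likely.

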6.11.2.3.2 PII

All PII records will be listed by participant, visit, and questionnaire type (self-report/parent proxy).

Absolute values and change from baseline will be summarized, overall and by confirmed objective response status (as defined with confirmed response rate in Section 4.1.1 using adjudicated values where appropriate), by visit and age cohort with self-report and parent proxy scores presented separately. The summaries presented will be number and percentage of participants with a non-missing score, mean, SD, median, minimum, and maximum values.

For PII a within-patient meaningful score change, or meaningful score difference (FDA, 2023), will be derived by anchor-based analysis of the trial's data, as described in the meaningful change threshold analysis plan (Version 1.0, dated 12Sep2023). The primary focus of this will be on if such a relevant difference exists at cycle 13.

Additionally, the number and percentage of participants with a change representing a clinically meaningful improvement (alongside associated 95% Clopper-Pearson confidence intervals) will be presented using the change from baseline of <-0.5*SD (using SD from baseline)(This is in-line with the difference used for analyzing PII on the selumetinib SPRINT study (Gross, 2018).) as well as change from baseline greater than the within-patient meaningful change threshold (i.e., derived by anchor-based analysis of the trial's data in accordance with the MCT SAP; see Section 5.8 above) in separate analyses.

In addition, within each age cohort, the proportion of participants reaching the anchor-based and distribution threshold will be analyzed in the subgroup of participants who have a confirmed objective response status versus the subgroup of those who do not. This is to further characterize the relationship between PRO improvement and the clinical endpoint of tumor response. The proportion of participants reaching the anchor-based (and distribution) thresholds will be summarized with 95% Clopper-Pearson Cls by confirmed objective response status, and the differences in the proportions of participants reaching the anchor-based/distribution thresholds between responders and non-responders will be tested using a Chi-Square test at a 5% significance level.

An MMRM will be fit separately by age cohort and questionnaire type, with change from baseline in PII score as the dependent variable, visit as a fixed effect and baseline PII score as a covariate. The covariance structure will be decided in the manner described in Section 6.11.2.2, and a Kenward-Roger approximation will be used for the degrees of freedom. This model will be fitted twice, once using only data through Cycle 13, and once through Cycle 24. Unscheduled and ET visits will be mapped to the closest scheduled tumor visit following the rules outlined in Table 13, and will only be included in the model if the participant has no other record at that timepoint. LS Means estimates will be presented with associated standard errors, 95% CIs and p-values by visit. Plots of the LS Means estimates over time with associated 95% CI bands will be presented separately by age cohort and questionnaire type for both models.

Box and whiskers plots of change from baseline will be presented by visit for adult cohort, pediatric cohort self-report and pediatric cohort parent proxy separately.

Document: S:\Q_146\Q_03974\MEK-NF-201\Prog_Stat\Documentation\SAP\MEK-NF-201 SAP v1.0.0.docx

Author:

A waterfall plot of change from baseline in PII will be presented by visit for adult cohort, pediatric cohort self-report and pediatric cohort parent proxy separately at cycles 5 and 13, with a line representing the respective within-patient meaningful change threshold derived by anchor-based analysis. This plot will be color-coded by confirmed objective response status.

Additionally, a sensitivity analysis will be performed on the PII results using the imputed data described in Section 5.5.1.2. The MMRM analysis described above will be performed with data up to Cycle 13. LS Means estimates, associated standard errors, 95% Cls and p-values will be presented by visit.

